2.4.3 Current status of economic evaluation of osteoporosis interventions

Pharmacological interventions—bisphosphonates, denosumab, and teriparatide—have been shown to be cost-effective in both men and women [63]. Schousboe et al. (2007) demonstrated cost-effective outcomes for BMD testing followed by bisphosphonate treatment in older men [64]. Fracture Liaison Services (FLS) are cost-effective across sexes [63]; Ito (2020) showed cost-effective osteoporosis screening in older men with a fall history [65]. Non-pharmacological interventions including vitamin D and calcium supplementation are cost-effective in older adults [63]; Hiligsmann et al. (2016) confirmed the cost-effectiveness of vitamin D–fortified dairy for fracture prevention in France [66]; and Johansson et al. (2008) demonstrated cost-effectiveness for community safety-promotion programmes in hip-fracture prevention [67]. Notably, no dedicated economic evaluation of RT exists—a gap this study aims to fill.

2.4.4 Challenges and methodological choices for economic evaluation of community exercise interventions

Community exercise economic evaluation faces five challenges, each paired with a targeted solution.

Challenge 1 — Cost fragmentation: Equipment depreciation, venue fees, and training costs are dispersed across multiple items. Solution: micro-costing with item-by-item accounting (e.g., smart terminal cost divided by 10 user-sessions; community worker time costed at hourly wage).

Challenge 2 — Delayed long-term effects: Fracture prevention requires 5–10 years of observation. Solution: Markov modelling extrapolation based on BMD improvement-to-fracture risk reduction, using FRAX® for risk calculation and assuming a conservative 3-year effect duration.

Challenge 3 — Multidimensional benefits: Exercise simultaneously improves function and psychological wellbeing. Solution: primary analysis using EQ-5D–derived QALYs, supplemented by CEA (ICER per 0.01 g/cm² BMD gain).

Challenge 4 — Adherence effects: Actual participation rates influence cost-effectiveness. Solution: attendance-adjusted costing with subgroup ICER analysis (50% vs. 80% attendance groups).

[figure not shown]
Challenge 5 — High uncertainty: Solution: probabilistic sensitivity analysis assigning

distributions to key parameters (cost $\pm 20\%$, effect $\pm 10\%$), with 1,000 Monte Carlo simulations generating CEAC curves.

The final methodological combination: RCT-based collection of 12-month cost/QALY data → Markov model projection of 10-year benefits → probabilistic sensitivity analysis for robustness verification.

Chapter 3 Research Hypotheses and Overall Conceptual Model

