2.2.3 Sources of heterogeneity in the evidence

Variability across studies arises from three principal sources. First, intervention protocol differences: training frequency of three sessions per week significantly improves BMD at multiple sites, interventions lasting ≥ 48 weeks significantly affect femoral neck and total hip BMD, and 40-minute sessions significantly improve lumbar spine BMD [42]. Second, participant characteristics: a 2021 study of 275 older adults aged 62–70 showed that following 9 weeks of progressive RT (three sessions per week), male participants gained 63 mm² in vastus lateralis cross-sectional area versus 20 mm² in females [45]. Third, measurement method differences: variations across DXA device models introduce BMD measurement error [46],

and different functional assessment tools yield varying sensitivity and specificity for fall prediction [47]. Standardisation of study design is therefore essential to reduce variability.

2.2.4 Gaps in the evidence for long-term community application, smart implementation, and individualisation

Three major evidence gaps persist. First, community long-term application evidence is insufficient: the majority of studies were conducted in controlled laboratory or clinical settings, with only three identified trials taking place in real-world community environments; community adherence rates and post-cessation effect maintenance remain unknown. Second, smart implementation research is absent: no study has systematically integrated intelligent devices and platforms (e.g., app-guided training, wearable sensors) into RT; most wearable devices serve monitoring functions only, and the impact of older adults' technology acceptance on outcomes has not been quantified. Third, individualised strategies are lacking: despite known responder variability, predictive tools to identify who will benefit most from RT are unavailable. These gaps collectively motivate the present study to validate long-term effectiveness in real community settings, explore smart-technology enhancement pathways, and develop individualised intervention tools.

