3.3.4 Detailed measurement schedule

表 3.3.4 Data measurement schedule 数据测量时间表						
Measurement field 测量领域	Specific measurement items 具体测量项目	T0	T1	T2	T3	备注
		Before intervention 干预前	4 months 4 个月	8 months 8 个月	14 months 14 个月	
Demography 人口学	Age, gender, education level, medical history, medication use	✓				Baseline collection only
Physical indicators	Height, weight, BMI	✓		✓	✓	Tracking changes

身体指标						
BMD 骨密度 DXA	Lumbar spine and hip BMD	✓	✓	✓	✓	4 months DXA As needed
Body functions 身体功能	SPPB Overall Rating	✓	✓	✓	✓	
	Overall balance	✓	✓	✓	✓	
	4-meter pace	✓	✓	✓	✓	
	5 Sit-to-Stand (5STS)	✓	✓	✓	✓	
	Grip strength (HGS)	✓	✓	✓	✓	Intermediary Indicators
Questionnaire 问卷调查	SF-36	✓	✓	✓	✓	
	FES-1	✓	✓	✓	✓	
	eHLQ、TAM	✓	✓	✓		Track
Implementation process 实施过程	Training compliance and dosage (platform log and manual log)		✓	✓		Continuous recording to stage nodes
Safety Monitoring 安全监测	Cumulative number of falls & adverse events			✓	✓	Summary
	New fracture				✓	
Behavior Tracking 行为追踪	Daily physical activity after intervention				✓	

Measurements are conducted at four time points: T0 (baseline, 1 week pre-randomisation) includes comprehensive demographic, clinical, functional, and questionnaire assessments; T1 (mid-intervention, 4 months) comprises streamlined assessments covering DXA (resources permitting), functional tests, adherence data, and questionnaires; T2 (end of intervention, 8 months) repeats the full baseline assessment battery plus cumulative adverse events; and T3 (follow-up, 20 months) evaluates long-term outcomes including new fractures, BMD maintenance, and post-intervention physical activity.

Chapter 4 Overall Methodology and Ethics

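### The Markov/QALY projection rests on an unsourced 3-year effect duration that is not among its named sensitivity parameters, and on 12-month trial data that match no scheduled visit

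*Protocol*

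**What the plan says.** Section 2.4.4 (Challenge 2) handles the delay in fracture benefit with a Markov model that converts BMD improvement into fracture-risk reduction, "assuming a conservative 3-year effect duration". It gives no source or derivation for the 3 years. The same section closes with the analysis chain: "RCT-based collection of 12-month cost/QALY data", then "Markov model projection of 10-year benefits", then a probabilistic sensitivity analysis. Challenge 5 names two parameters for that analysis, cost at ±20% and effect at ±10%. Challenge 3 makes QALYs derived from the EQ-5D the primary economic measure.

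On persistence, section 2.2.4 says of the published evidence that "community adherence rates and post-cessation effect maintenance remain unknown".

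On timing, section 3.3.4 says "Measurements are conducted at four time points". These are baseline, 4 months, 8 months (the end of the intervention) and T3. The schedule table puts T3 at 14 months; the text below it says "T3 (follow-up, 20 months) evaluates long-term outcomes including new fractures, BMD maintenance, and post-intervention physical activity". DXA is scheduled in both arms at T2 and T3. Sections 1.3.4 and 1.4.1 place a 12-month maintenance phase, once monthly, after the 8 months of training.

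**The concern.** Over a 10-year projection, the length of time for which a BMD gain is credited largely determines how much fracture benefit the model counts. The protocol fixes that length, calls it conservative, and elsewhere describes the same quantity as unknown. Regular training lasts 8 months, so most of the credited 3 years falls after it has stopped.

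Two further features compound this. The sensitivity parameters that are named leave out duration, so the acceptability curve may be too narrow. And a 12-month cost and QALY value cannot be read off any visit: it would have to be interpolated between T2 and T3, across the point where regular training ends and the course is hardest to predict.

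At stake is the credibility of the extrapolated cost per QALY, which sections 1.3.4 and 1.4.4 present as a main contribution of the study.

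**Working it through.** The protocol gives no figures from which 3 years could be derived, so there is no calculation of its own to reproduce. The check has three parts.

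**1. The 12-month input against the visits.** Visit months are 0, 4, 8 and 14 (table) or 0, 4, 8 and 20 (text). Month 12 is in neither list. The only other mention of 12-month follow-up is an exclusion criterion in section 4.2.2, which is not a visit. The schedule lists the SF-36, FES-I, eHLQ and TAM, but no EQ-5D at any visit, so as written the planned QALYs have no scheduled source at month 12 or at any other time.

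**2. How much of the 3 years the trial can observe.**
- T3 lies 14 − 8 = 6 months (table) or 20 − 8 = 12 months (text) after the end of training.
- Counted from baseline, follow-up covers 14/36 = 39% or 20/36 = 56% of the 3 years.
- The rest is assumption under either date.

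**3. How much duration matters (illustration only).** Assumptions: the BMD effect builds linearly to its full size over 8 months, the benefit is proportional to it and arises only through it, there is no discounting, and the 3 years run from baseline with a flat effect after month 8. All scenarios share the same build-up.
- Build-up: 0.5 × 8/12 = 0.333 effect-years.
- Flat to month 36: 0.333 + 28/12 = 2.667.
- Fade to zero over 12 months after training: 0.333 + 0.5 × 1 = 0.833.
- Fade to zero over 24 months: 0.333 + 0.5 × 2 = 1.333.
- Ratios: 2.667/0.833 = 3.2 and 2.667/1.333 = 2.0.
- Effect varied by ±10%: 0.9 × 2.667 = 2.40 to 1.1 × 2.667 = 2.93. Neither fade scenario comes near this range.

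Two readings left open by the protocol change the size:
- If the effect declines linearly to zero at month 36, the credit is 0.333 + 0.5 × 28/12 = 1.5, and the ratios fall to 1.5/0.833 = 1.8 and 1.5/1.333 = 1.1.
- If the 3 years start at month 8 with a flat effect, the credit is 0.333 + 3 = 3.333, and the ratios are 4.0 and 2.5.

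The error could also run the other way. A flat effect to year 5 gives 0.333 + 52/12 = 4.667, and the 3-year figure would then understate the benefit.

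**The case against.** The strongest reply is that section 2.4.4 is a short outline in a literature and theory chapter, and that waning functions, scenarios and the full parameter list usually belong in an analysis plan, which is not shown here. That stands in part. A reader might infer that the model ignores the T3 data or holds duration fixed. The protocol does not say so: no passage links T3 BMD to the model, but none excludes it, and naming two parameters does not prove that there are no others. What remains is not an omission. The protocol states a value, a favourable label, two sensitivity ranges and an input horizon that fits no visit.

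A second reply is that 3 years is conservative against a 10-year horizon, because the last 7 years earn nothing. That probably explains the word. It does not make the value conservative relative to 8 months of training when persistence is unknown.

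A third is that T3 does not measure what the model needs. A reader might take the T2-to-T3 course as a direct measurement of persistence after training stops. It is not: once-monthly maintenance runs in that period, and only 6 or 12 months are seen. It is still better evidence than an unsourced constant, provided that it is described for what it is.

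Finally, a reader might conclude that the study's whole economic case, or its insurance decision rule, depends on the 3 years. The documents do not support that. H6 (section 3.2.6) and Sub-study 6 (section 1.4.2) are expressed per unit of BMD and need no extrapolation, and the decision tree in section 1.4.5 does not say which ICER it uses.

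**Conclusion.** The point holds for the Markov/QALY projection. Its effect duration is unsourced and labelled conservative although persistence is called unknown, duration is not among the sensitivity parameters named, and its 12-month input matches no visit under either T3 date.

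Under the stated assumptions, with the 3 years counted from baseline, the credited benefit could be too high by at most about 3.2-fold (12-month fade) or 2.0-fold (24-month fade). These are upper bounds because any QALY gain through function or wellbeing, which Challenge 3 expects, would dilute them; for the same reason they do not carry over directly to cost per QALY. They show that plausible differences in duration lie far outside ±10%, not that the benefit is in fact overstated.

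The primary clinical comparison and the BMD-based ICER are untouched. The change is worth making because it is cheap and the projection is aimed at policy.

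**What to change.** 1. Reconcile the T3 date (14 months in the table, 20 in the text) before anything is tied to it.
2. Replace the 12-month horizon by one that ends at a scheduled visit: T2 for the within-trial analysis and T3 for the extended one. Count maintenance-phase costs to the same date. Reconcile the EQ-5D-based QALYs with the schedule, which lists no EQ-5D.
3. Use the between-arm BMD differences at T2 and T3 to inform waning, described as persistence under once-monthly maintenance. State when the effect period starts and what shape the decline takes. Put duration or waning, with its uncertainty, into the probabilistic analysis. Keep 3 years as a scenario and drop the word conservative.

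The cost is a rewording of section 2.4.4, a correction to the schedule and a modelling change. The BMD data are already planned; collecting the EQ-5D, if that is how the QALYs are reconciled, would add a short questionnaire. The extrapolated ICER may look less favourable and must wait for T3, and waning beyond T3 remains an assumption to be varied.

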2.4 Cost-Effectiveness and Health Economics Framework

2.4.1 Basic types of health economic evaluation

Health economic evaluation assists decision-makers in determining whether medical interventions warrant investment. Three principal types exist. Cost-effectiveness analysis (CEA) compares the costs and natural health outcomes of different interventions—for example, the cost per 1% BMD improvement or per fracture prevented. Cost–utility analysis (CUA) uses the quality-adjusted life year (QALY) as the effectiveness unit, combining survival time and quality of life; cost per QALY gained (ICER) enables cross-disease comparison. Cost–benefit analysis (CBA) monetises health outcomes, directly comparing the monetary value of averted fractures with intervention costs; however, the monetisation of health value remains controversial and limits practical application.

2.4.2 The concept, calculation, and interpretation of the incremental cost-effectiveness ratio (ICER)

ICER is the core metric for evaluating the economic merit of an intervention. It is calculated as: $ICER = (\text{Cost of intervention group} - \text{Cost of control group}) / (\text{Effect of intervention group} - \text{Effect of control group})$. For example, if smart RT costs CNY 500 per person, control costs CNY 100, and the intervention group gains 0.05 QALY with no change in controls, then $ICER = (500 - 100) / (0.05 - 0) = \text{CNY } 8,000/\text{QALY}$.

ICER must be compared against a willingness-to-pay (WTP) threshold. The internationally accepted benchmark is one to three times per-capita GDP. China’s 2024 per-capita GDP of approximately CNY 95,000 [62] yields a threshold of CNY 285,000/QALY (three times GDP). If ICER falls below this threshold, the intervention is considered cost-effective. Special cases: when the intervention is both less costly and more effective (negative ICER), it is “dominant”; when it is costlier and less effective, it should be rejected. Uncertainty is assessed through bootstrap resampling (1,000 iterations) to generate a cost-effectiveness acceptability curve (CEAC).

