3.1 Overall Logic Model

3.1.1 Graphical explanation of core elements

The logic model systematically depicts each component of the research and their interconnections. At the “input” level, the study invests essential resources—community training venues, smart RT equipment, and professional supervisors—while accounting for participant characteristics such as age, sex, baseline health status, and eHealth literacy. The “activities” component refers to the smart RT intervention delivered by trained community workers following prescribed frequency, intensity, and duration protocols. Direct “outputs” include training adherence (attendance rate, training completion rate) and actual training “dose” (cumulative training volume), reflecting intervention execution fidelity. These outputs generate “short-term outcomes”: improved BMD, enhanced physical function (muscle strength, balance), and increased QoL scores after 8 months. Mechanistic indicators, notably grip-strength change (Δ HGS), are also monitored to explore the mediating role of muscle strength. In the long term, the intervention is expected to reduce fracture risk and demonstrate “cost-effectiveness” at the health-economic level. Several moderating factors—community environment support, technology acceptance, socioeconomic status, and the digital divide—may influence adherence and effect magnitude.

In Figure 3.1, arrows represent causal pathways: from input resources and participant

characteristics, through the RT intervention, influencing adherence and dose, producing short-term improvements in physical and quality-of-life outcomes, and ultimately accumulating into long-term fracture-risk reduction and cost-effectiveness.

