3.3 Operationalisation of Core Variables and Measurement Time Points

3.3.1 Independent variables

Core independent variables include: (1) intervention allocation (smart RT intervention group vs. health education control group), the primary independent variable; (2) baseline

demographic and clinical characteristics (age, sex, education, BMI, T-score, fracture history, comorbidities), serving as covariates; (3) technology acceptance indicators, assessed via the eHLQ and TAM scales; and (4) intervention process indicators—adherence (proportion of sessions completed) and dose (cumulative training volume).

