4.1 Study Design Overview

4.1.1 Primary study design

This study employs a two-arm, parallel-group, assessor-blinded randomised controlled trial (RCT), with 1:1 allocation to the intervention and control groups. Outcome assessors are blinded to group assignment to minimise measurement bias. The protocol and reporting adhere to the CONSORT 2010 Statement, including transparent documentation of randomisation sequence generation, allocation concealment, blinding, and participant flow.

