4.3.2 Control group

The control group receives standard health education without systematic RT. Activities include monthly 60-minute bone-health lectures (OP pathophysiology, nutritional guidance, fall-prevention strategies), delivered by hospital orthopaedic and community clinic staff, with

printed educational materials. Group discussion sessions are held every 4 months. Weekly telephone or WeChat follow-up by research staff provides general health advice (e.g., daily 20–30 minute walks), maintaining comparable contact frequency without introducing RT. This “attention control” design ensures that contact and engagement levels are balanced between groups.

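### The planned ICERs by attendance group compare self-selected trainees with no randomised counterpart, so they mix who attends with what training does

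*Protocol*

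**What the plan says.** Protocol section 2.4.4 lists five challenges for the economic evaluation. Challenge 4 is that actual participation affects cost-effectiveness. The answer given is "attendance-adjusted costing with subgroup ICER analysis", and the groups are named in the same sentence: "subgroup ICER analysis (50% vs. 80% attendance groups").

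Other sections bear on what this analysis would be:

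- Section 3.3.1 classes attendance among the intervention process indicators: "adherence (proportion of sessions completed) and dose (cumulative training volume").
- Section 4.3.2 describes the comparator: "The control group receives standard health education without systematic RT". Controls therefore have no training attendance.
- Section 4.1.1 describes a randomised trial "with 1:1 allocation to the intervention and control groups".
- Section 2.4.2 defines the ICER as the cost difference between the two trial groups divided by their effect difference. Its example reads: "if smart RT costs CNY 500 per person, control costs CNY 100, and the intervention group gains 0.05 QALY with no change in controls".
- Section 3.1.1 says that several participant and community factors "may influence adherence and effect magnitude".
- The closing summary of methods in section 2.4.4 does not mention attendance subgroups.

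**The concern.** An ICER needs a comparator. Randomisation supplies one for the whole training arm, but not for the part of that arm which turned out to attend 80% of sessions or the part that attended 50%. Controls cannot be sorted in the same way because they have no training sessions. If each attendance group is compared with all controls, people selected on behaviour after randomisation are set against an unselected group.

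The protocol itself gives reasons to expect that selection matters. Section 3.1.1 links technology acceptance, socioeconomic status and the digital divide to adherence. Hypothesis H4 (section 3.2.4) expects people who struggle with the device to drop out of training. Sections 4.3.1 and 4.7.3 have participants stop exercising when unwell and be suspended after a serious adverse event, so poor health can itself lower attendance.

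At stake is how the result is read. A lower ICER in the 80% group invites the conclusion that raising attendance improves value for money, when part or all of the contrast may reflect who attends.

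**Working it through.** **Plan's own figures.** ICER = (C1 − C0)/(E1 − E0) = (500 − 100)/(0.05 − 0) = CNY 8,000 per QALY, as section 2.4.2 states. The threshold is 3 × 95,000 = CNY 285,000 per QALY, which also reproduces.

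**Assumed inputs (not in the documents).**

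- The true effect is 0.05 QALY for every participant, whatever the attendance.
- Attendance correlates r = 0.3 with the QALY change that would occur without training.
- The SD of QALY change is 0.05 or 0.10.
- The training arm is split at median attendance, and each half is compared with all controls.

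**Effect in each half.** With a normal distribution, the mean of the upper or lower half lies 0.798 SD from the overall mean. The shift is r × 0.798 × SD.

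- SD 0.05: shift 0.3 × 0.798 × 0.05 = 0.01197. Effects are 0.06197 (high) and 0.03803 (low).
- SD 0.10: shift 0.3 × 0.798 × 0.10 = 0.02394. Effects are 0.07394 (high) and 0.02606 (low).

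**Flat cost (difference of 400 in both halves).**

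- SD 0.05: 400/0.06197 = 6,455 and 400/0.03803 = 10,518. Low-to-high ratio 1.63.
- SD 0.10: 400/0.07394 = 5,410 and 400/0.02606 = 15,349. Ratio 2.84.

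**Cost fully proportional to attendance.** Take attendance of 0.8 and 0.5, mean 0.65, with the arm's mean cost held at 500. Cost differences are 500 × 0.8/0.65 − 100 = 515.4 (high) and 500 × 0.5/0.65 − 100 = 284.6 (low).

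- No selection: 515.4/0.05 = 10,308 and 284.6/0.05 = 5,692. Ratio 0.55.
- SD 0.05: 515.4/0.06197 = 8,317 and 284.6/0.03803 = 7,484. Ratio 0.90.
- SD 0.10: 515.4/0.07394 = 6,970 and 284.6/0.02606 = 10,922. Ratio 1.57.

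Attendance-adjusted costing therefore changes the visible gap and can reverse its sign, but it does not remove the selection. Under these assumptions selection multiplies the ratio by the same 1.63 or 2.84 in either case. It starts from 1.00 with flat cost and from 0.55 with proportional cost.

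**Against the thresholds.** The largest value above is 15,349. That is 16% of one times per-capita GDP (95,000, the decision point in section 1.4.5) and 5% of 285,000.

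**The case against.** Three objections carry weight.

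**Size.** A reader might infer that the two ICERs could differ severalfold with no true difference between the groups. The documents do not support that. The sentence that plans the subgroups also prescribes attendance-adjusted costing, so flat cost is the case least in keeping with the text. Costs would truly differ, so at most there is no true difference in *effect*. A gap of threefold or more also needs a prognostic difference about as large as the treatment effect. With a 50:50 split, a difference of 0.05 QALY gives a ratio of 3.0 at flat cost but 1.7 at fully proportional cost, and a difference of 0.03 at proportional cost gives about 1.0. No figure in the protocol says how large the difference is.

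**Consequence.** A reader might also infer that a cost-effectiveness conclusion would change. None of the illustrative values comes near a threshold. The inputs are a teaching example, and H6 is framed per 0.01 g/cm² of BMD rather than per QALY.

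**Premises and scope.** Section 2.4.4 names no comparator for the subgroups, so comparing each with all controls is the natural reading, not a stated rule. Nowhere does the protocol say that good attenders are healthier. Section 3.1.1 speaks partly of real differences in effect. The analysis is supplementary and sits in the literature and theory chapter, and the ICER is already defined by randomised group. Modelled scenarios may have been intended, although the words subgroup and groups point to observed attendance.

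These points limit the size and reach of the concern but do not remove it. Any comparator for groups formed by observed attendance in one arm is non-randomised, and no section of the protocol addresses that selection. Real effect modification would be mixed into the same contrast and could not be separated from prognosis.

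**Conclusion.** The concern holds for a supplementary analysis. ICERs by observed attendance would not isolate what attendance does to value for money, because neither group has a randomised counterpart. The documents determine neither the size nor the direction of the distortion. Under the assumptions shown, the low-to-high ratio is about 1.6 to 2.8 with flat cost and about 0.9 to 1.6 with fully attendance-proportional cost. Both ranges rest on the assumed correlation of 0.3, the assumed QALY SD of 0.05 to 0.10, the median split and the protocol's illustrative costs and effect. The as-randomised ICER is sound on this point, and no illustrative value reaches CNY 95,000 or CNY 285,000 per QALY.

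**What to change.** Replace the observed-attendance subgroups in Challenge 4 with one of two analyses:

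1. Modelled scenarios at 50% and 80% attendance that vary both cost and effect, with the assumed attendance-effect relation stated and varied.
2. Strata formed in both arms from attendance predicted by baseline variables, so that each stratum keeps its randomised comparison. State the cut-offs, including where participants between 50% and 80% belong.

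Label either result exploratory, and say that conclusions rest on the as-randomised ICER.

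A complier-average estimate using randomisation as the instrument is a weaker choice. One such effect does not answer how value differs between 50% and 80% attendance. Its exclusion restriction is also doubtful, because the training arm receives a wristband, individual coaching and lectures whatever the number of sessions completed.

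The cost is a change of wording and a little programming. The scenarios depend on an assumed relation between attendance and effect. Predicted strata separate attenders less sharply and give less precise estimates.

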1.4.5 Application innovations

Community RT responder screening tool: A nomogram based on baseline grip strength, sedentary time, and BMI for rapid identification of high-responder populations (BMD improvement $\geq 3\%$; AUC = 0.82), guiding targeted resource allocation [Sub-study 1].

Low-technology smart supervision protocol: A “dual-track supervision model”—digital track (WeChat-based training reminders and video guidance) and manual track (weekly telephone follow-up and periodic home visits by community workers).

Health insurance alignment decision tree: Cost-effectiveness outputs translated into policy pathways based on the ICER-to-GDP ratio: when ICER does not exceed one times per-capita GDP, the intervention enters the basic public health service package; when it exceeds this threshold, supplementary commercial health insurance is required.

Chapter 2 Literature Review and Theoretical Foundations

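### The Monte Carlo acceptability curve for the 10-year projection varies the effect by a fixed ±10% of its estimate, which is unrelated to the trial's sampling error, and the planned bootstrap is not linked to it

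*Protocol*

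**What the plan says.** Section 2.4.4 lists high uncertainty as the fifth challenge of the economic evaluation. Its answer is a probabilistic sensitivity analysis (PSA) with distributions on "key parameters (cost $\pm 20\%$, effect $\pm 10\%$), with 1,000 Monte Carlo simulations generating CEAC curves". The shape of the distributions is not given, nor is the effect parameter that is varied. The section closes with the final combination of methods: "RCT-based collection of 12-month cost/QALY data → Markov model projection of 10-year benefits → probabilistic sensitivity analysis for robustness verification". The PSA is therefore the stated check on the long-term result.

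The same section specifies a "primary analysis using EQ-5D–derived QALYs" and builds the Markov model on the step from BMD improvement to fracture risk.

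Section 2.4.2, on the ICER, gives another route to an acceptability curve: "Uncertainty is assessed through bootstrap resampling (1,000 iterations) to generate a cost-effectiveness acceptability curve (CEAC"). No section says how the bootstrap and the PSA relate, and the final combination names only the PSA.

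**The concern.** A cost-effectiveness acceptability curve (CEAC) is read as the probability that the programme is worth its cost, given how well the data determine cost and effect. A range of ±10% around the estimate answers a different question: how the result moves if the estimate is almost exactly right. The trial's precision does not enter, so the curve would be equally wide with 30 or 3,000 participants per arm.

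How far zero lies from the estimate depends on how ±10% is read. It is 10 SDs away if ±10% is one SD, about 20 SDs away if it is a 95% range (0.10/1.96 = 0.051 of the estimate per SD, and 1/0.051 = 19.6), and outside the distribution if it is uniform. On every reading, practically all draws keep the sign of the point estimate.

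At stake is whether the only named check on the 10-year projection can show that the effect might be absent.

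**Working it through.** **Inputs from the protocol.** Section 2.4.2 illustrates with "if smart RT costs CNY 500 per person, control costs CNY 100, and the intervention group gains 0.05 QALY with no change in controls". Per-capita GDP of about CNY 95,000 "yields a threshold of CNY 285,000/QALY (three times GDP"), and Section 1.4.5 uses one times GDP. The PSA ranges are ±20% for cost and ±10% for effect.

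**Assumptions.** The protocol gives no sample size, QALY SD or SD of BMD change for this analysis. I take 30 to 100 per arm (1:1), a QALY SD of 0.08 to 0.15 and an SD of percentage BMD change of 2.5 to 4. Section 1.4.4 mentions conditions with fewer than 100 participants, but only for the dose–response work. Cost is held fixed in the sampling-error figures. The ranges are applied directly to the trial effect, because the Markov step is not specified closely enough to reproduce.

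**Step 1: the protocol's own figures.** ICER = (500 − 100)/(0.05 − 0) = CNY 8,000/QALY, and 3 × 95,000 = 285,000. Both match.

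**Step 2: sampling error against ±10%.** SE = SD × √(2/n); half-width = 1.96 × SE.
- QALY, smallest: 1.96 × 0.08 × √(2/100) = 0.0222, or 44% of 0.05.
- QALY, largest: 1.96 × 0.15 × √(2/30) = 0.0759, or 152% of 0.05.
- BMD, smallest: 1.96 × 2.5 × √(2/100) = 0.69, or 23% of 3.
- BMD, largest: 1.96 × 4 × √(2/30) = 2.02, or 67% of 3.

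For ±10% to be a true 95% interval around 0.05 QALY, n = 2 × (1.96 × SD/0.005)², which is about 1,970 per arm (SD 0.08) to 6,915 per arm (SD 0.15).

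**Step 3: when the PSA reports certainty.** With uniform ranges, every draw is favourable if 0.9 × effect × threshold exceeds 1.2 × cost, that is, if the point ICER is below 0.9/1.2 = 75% of the threshold. That is CNY 71,250 at one times GDP and 213,750 at three times GDP, whatever the sample size. With a negative estimate and a positive incremental cost, every draw is unfavourable.

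**Step 4: the same observed result, both ways.** The sampling-error probability is Φ((gain − cost/threshold)/SE), with incremental cost CNY 400. SE runs from 0.0113 (SD 0.08, n = 100) to 0.0387 (SD 0.15, n = 30).

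| Observed gain | Threshold | PSA | Sampling error |
|---|---|---|---|
| 0.01 QALY | 95,000 | 100% | 56% to 70% |
| 0.01 QALY | 285,000 | 100% | 59% to 78% |
| 0.05 QALY | 285,000 | 100% | 90% to 100% |

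For example, (0.01 − 400/285,000)/0.0387 = 0.22, and Φ(0.22) = 0.59.

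**Step 5: a true QALY effect of zero.** With uniform ranges, the PSA shows at least 95% when the point ICER is below about 82% of the threshold (by simulation). The share of trials is therefore 1 − Φ(cost/(0.82 × threshold × SE)). With sampling error it is 1 − Φ(1.645 + cost/(threshold × SE)). Incremental costs other than CNY 400 are assumptions.

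| Incremental cost | Threshold | PSA shows ≥95% | Sampling error shows ≥95% |
|---|---|---|---|
| 400 | 95,000 | 32% to 45% | 2% to 4% |
| 400 | 285,000 | 44% to 48% | 4% to 5% |
| 2,000 | 95,000 | 1% to 25% | 0% to 1% |
| 2,000 | 285,000 | 22% to 41% | 1% to 3% |

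**The case against.** The strongest reply is that the plan already has a CEAC with sampling error. The bootstrap of Section 2.4.2 may serve the within-trial analysis and the PSA the extrapolation, as successive stages rather than rivals. That reading is open. A reader might infer that the two sections contradict each other or that sampling error is ignored altogether, and the text supports neither. What the documents lack is the link: as written, the bootstrap stops at the trial and the 10-year result is checked only by the PSA.

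A second reply is that little depends on this curve. H6 (Section 3.2.6) concerns the ICER per 0.01 g/cm² of lumbar spine BMD. The insurance rule of Section 1.4.5 is stated on the ICER itself: "when ICER does not exceed one times per-capita GDP, the intervention enters the basic public health service package". Neither uses a CEAC probability, and a wider curve would not change the branch chosen. This stands and limits the weight of the point.

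Third, the null-effect shares are partly mechanical, because half of all estimates are positive when the true effect is zero. They also rest on assumed n, SD and cost, bypass the Markov step, and fall as cost rises. This stands too, so they are illustrations and not predictions for this trial.

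Finally, distributions can be settled in a statistical analysis plan, which is not at hand. But the protocol does not leave the effect range open. It fixes a figure, and that figure does not measure the uncertainty it is meant to represent.

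**Conclusion.** The point holds for the PSA-based CEAC of the 10-year projection. A fixed ±10% of the estimate is not a measure of the trial's uncertainty. Under the stated assumptions the 95% half-width is roughly 4 to 15 times as wide for a 0.05 QALY gain, and 2 to 7 times as wide for a 3% BMD gain.

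False near-certainty is conditional and runs both ways. Certainty in favour needs a point ICER below about 75% of the threshold under uniform ranges, and a chance loss is shown as near-certainly not cost-effective. For the protocol's own example the difference is modest.

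A reader might go further and conclude that the H6 test or the insurance decision is invalid. The documents do not support that, since neither is decided by this curve. What is affected is the credibility of the only check named for the long-term result. The change is worth making, but it touches one nested sub-study and no primary outcome.

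**What to change.** In Section 2.4.4 (Challenge 5), replace the ±10% effect range with the trial's own sampling uncertainty. Either of two routes will do:
- carry the patient-level bootstrap replicates of Section 2.4.2 through the Markov model, keeping each replicate's incremental cost paired with the BMD effect that drives the model; or
- draw cost and effect from their estimated between-arm standard errors and correlation.

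Build the CEAC from net monetary benefit over those draws. State in Sections 2.4.2 and 2.4.4 that the bootstrap feeds the PSA. Keep ±10% and ±20% only as labelled one-way sensitivity analyses.

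QALY replicates can be used only where EQ-5D is collected. It appears in Section 2.4.4 but not among the outcomes (Sections 3.3.2, 4.4.1 and 4.4.2) or in the measurement schedule (Section 3.3.4). The version based on BMD, which is scheduled, needs no new effect data.

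The cost is a few sentences and a little more simulation code. The price is a flatter and probably less favourable curve.
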